4.3. Analysis Exclusion Criteria

4.3.1. Patients excluded from safety analysis

If there are overlapping reasons for exclusion and the reasons for exclusion should be prioritized, the reasons for exclusion from the safety analysis should be assigned in the following order:

Code	Safety Excluded from analysis	Priority Rank	Conditions for exclusion	Logic Judgment
S1	Outside the survey/registration period	1	
 • The date of completion of administration of this drug/the date of last observation is outside the survey period • Date of enrollment is outside the enrollment period 	○
S2	Outside the contract period	2	
 • The date of registration is outside the contract period. 	○
S3	This drug naïve	3	
 • Patients with no description at all in the Dosage and Administration section of this drug or all descriptions of dosage are 0 	○
S4	No visits after first dose (SC only)	4	
 • The reason for discontinuation/completion of administration in the [Status of continuation of administration of this drug at the end of the observation period] is "No 	○

Code	Safety Excluded from analysis	Priority Rank	Conditions for exclusion	Logic Judgment
			visits after the first dose"	
S5	Adverse event data missing	5	• Cases for which [Presence/absence of adverse event] is “Unknown ” or blank and there is no adverse event data	○
S6	Same case (co-examination/hospital transfer)	6	• A case judged to be the same case after consultation/transfer to another hospital	×
S7	Same case (duplicate description)	7	• Cases in which the same information is entered redundantly and judged to be the same case	×
S8	Others (safety)	8	• Exclusion items determined by the case review committee for reasons other than the above	×

4.3.2. Patients excluded from efficacy analysis

If there are overlapping reasons for exclusion and the reasons for exclusion should be prioritized, the reasons for exclusion from the efficacy analysis should be assigned in the following order:

Code	Efficacy Excluded from analysis	Priority Rank	Conditions for exclusion	Logic Judgment
E1	OFF LABEL USE	1:SLE 2: Children	• Indication other than “systemic lupus erythematosus ” • Cases used in pediatric patients	×
E2	Others (efficacy)	3	• Exclusion items determined by the case review committee for reasons other than the above	×

4.4. Handling of missing data

4.4.1. Data Imputation

4.4.2 will be followed for missing data, and no other data imputation will be performed.

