4.4.2. SELENA SLEDAI, PGA

With the LOCF approach, if there is no data at the time of discontinuation/completion after Week 52 or Week 24 from the start of administration of this drug, the data will be imputed with the data up to Week 52 from the start of administration of this drug.

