4.4.3. Missing continuous data

If there is a missing value in the tabulation of continuous data, it will be excluded from the tabulation. If continuous data are available at multiple time points, only the missing time points will be excluded. If continuous data are classified into categories, follow "4.4.4 Categorical Data."

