4.10. Responders

A responder is defined as a case where this drug treatment start date and post-treatment assessments are present and the following conditions are met:

Efficacy assessments	Responder definition
SELENA SLEDAI (Used for calculation of efficacy percentage)	≥ 4 decrease in score from baseline
PGA score	≥ 0.3 (10 mm) decrease from baseline
LLDAS (Lupus Low Disease Activity State)	1. SELENA-SLEDAI ≤ 4 and no major active organ involvement (renal, central nervous system, cardiopulmonary, vasculitis, pyrexia) on SELENA-SLEDAI, without hemolytic anemia or active gastrointestinal lesions reported as adverse events.
	2. No new signs or symptoms as compared to the last SELENA-SLEDAI assessment.
	3. PGA score ≤ 1 (33 mm)

Efficacy assessments	Responder definition
	4. Corticosteroid dose ≤ 7.5 mg/day at time of assessment
	5. Use of the same immunosuppressant as compared with prior medication. No unapproved drugs of rituximab, anifrolumab, ustekinumab, or baricitinib are used as concomitant medications. The use of anifrolumab with this drug initiated on 2021/9/27 or later is allowed.
LLDAS Adverse Events	Haemolytic anaemia: 10018916 (PT code) Active gastrointestinal lesions: to be defined in a separate document
Corticosteroid Reduction at Week 40~52	Average daily dose Proportion of patients who were able to reduce their average daily steroid dose by $\geq 25\%$ and ≤ 7.5 mg/day from baseline at Week 40~52 (in patients with baseline average daily steroid dose > 7.5 mg/day). Subjects who discontinued or completed administration of this drug before Week 52 will be classified as non-responders.

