6.4.2. Changes in responder rates (LOCF) (Tables 3.021, 3.0211, 3.0212, 3.022, 10.2)

Analyzed:	Efficacy analysis population
Analysis details:	
The number of responders/non-responders and the responder rate will be calculated in chronological order for each efficacy endpoint (SELENA SLEDAI score, PGA score, LLDAS, reduction of steroid dose at Week 40~52). 95% confidence intervals will be calculated for assessment at discontinuation/completion (LOCF).
 
Data will also be summarized by the presence or absence of severe lupus nephritis, presence or absence of severe central nervous system lupus, and route of administration as reasons for this drug use.
 
For data at discontinuation/completion (LOCF), the same analysis will be performed by patient characteristic.
 
For steroid dose reduction at Week 40~52, subjects whose baseline average daily steroid dose is > 7.5 mg/day will be included.

Chronological order:	Week 24, Week 52, at discontinuation/completion (LOCF), and Week 40~52 (steroid dose reduction at Week

40~52)

Patient characteristics:	
• SELENA SLEDAI (baseline): $\leq 9, \leq 10$• Anti-dsDNA antibody (baseline) [IU/mL]: $<30, 30 \leq$• Complement Levels:
Low C3 and/or Low C4Other than the above• C3 (baseline) [mg/dL] ($<90, 90 \leq$)• C4 (baseline) [mg/dL] ($<10, 10 \leq$)• Use of steroids at the start of treatment: No, Yes• Baseline steroid [mg/day]: $\leq 7.5, 7.5 <$• Immunosuppressant use: No, Yes
--------------------------	--

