6.4.3. Changes over time in efficacy endpoints (LOCF) (Tables 3.03, 3.0301, 3.0302)

Analyzed:	Efficacy analysis population
Analysis details:	
Summary statistics of (SELENA SLEDAI, PGA, Lupus Impact Tracker) will be calculated for each efficacy endpoint in chronological order.
 
Data will also be summarized by the presence or absence of severe lupus nephritis and by the presence or absence of severe central nervous system lupus as the reason for this drug use.

Calculation items:	Score, change, percent change
Chronological order:	Baseline, Week 24, and Week 52, and at discontinuation/completion (LOCF)

6.4.4. Change in the proportion of responders per system organ class in SELENA SLEDAI score (LOCF) (Tables 3.04, 3.0401, 3.0402)

Analyzed:	Efficacy analysis population
Analysis details:	
SELENA SLEDAI score The proportion of patients with a decrease in SELENA SLEDAI score from baseline will be calculated over time for each organ system index.
 
Data will also be summarized by the presence or absence of severe lupus nephritis and by the presence or absence of severe central nervous system lupus as the reason for this drug use.

CONDITION:	Patients with baseline SELENA SLEDAI score > 0 will be included.
Chronological order:	Week 24, Week 52, or at discontinuation/completion (LOCF)

6.4.5. Proportion of patients with worsening of SELENA SLEDAI score by organ system over time (LOCF) (Tables 3.05, 3.0501, 3.0502)

Analyzed:	Efficacy analysis population
Analysis details:	
SELENA SLEDA score The proportion of subjects with worsening of SELENA SLEDAI score from baseline will be calculated over time for each organ system index.

Data will also be summarized by the presence or absence of severe lupus nephritis and by the presence or absence of severe central nervous system lupus as the reason for this drug use.

CONDITION: Patients with baseline SELENA SLEDAI score ≥ 0 will be included.

Chronological order: Week 24, Week 52, or at discontinuation/completion (LOCF)

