6.4.6. Changes in Lupus Impact Tracker scores (LOCF) (Table 3.06)

Analyzed: Efficacy analysis population

Analysis details: For Lupus Impact Tracker scores, summary statistics will be calculated for each item in chronological order.

Calculation items: Score, change, percent change

Chronological order: Baseline, Week 24, and Week 52, and at discontinuation/completion (LOCF)

6.4.7. Changes over time in laboratory tests (Anti-dsDNA, C3, C4, CH50, protein/creatinine ratio) (Table 3.07)

Analyzed: Efficacy analysis population

Analysis details: For anti-dsDNA antibody, C3, C4, CH50, and protein/creatinine ratio, summary statistics will be calculated chronologically for each item.

Chronological order: Baseline, Week 24, and Week 52, and at discontinuation/completion (LOCF)

6.4.8. Number of days with steroid dose reduction to ≤ 7.5 mg/day and/or $\geq 50\%$ reduction from baseline (Table 3.11)

Analyzed: Efficacy analysis population

Analysis details: Summary statistics will be calculated over time for the number of days with steroid dose reduction to ≤ 7.5 mg/day and/or at least a 50% reduction from baseline.

CONDITION: Patients with baseline average daily steroid dose >7.5 mg/day will be included.

Chronological order: Weeks 4, 8, 12, 16, 20, 24, 28, 32, 36, 40, 44, 48, and 52

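### Lupus Impact Tracker and laboratory outputs have an LOCF time point that the SAP's own imputation rule does not allow

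*SAP*

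**What the plan says.** Three rules in the SAP govern missing effectiveness values.

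- Section 4.4.1: "4.4.2 will be followed for missing data, and no other data imputation will be performed".
- Section 4.4.2 has the heading "4.4.2. SELENA SLEDAI, PGA". When no discontinuation/completion record exists, "the data will be imputed with the data up to Week 52 from the start of administration of this drug".
- Section 4.4.3: "If there is a missing value in the tabulation of continuous data, it will be excluded from the tabulation". It adds that, for repeated measurements, only the time point with the gap is dropped.

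The output specifications ask for more than these rules provide. Section 6.4.3 (Table 3.03 series, titled LOCF) states: "Summary statistics of (SELENA SLEDAI, PGA, Lupus Impact Tracker) will be calculated for each efficacy endpoint in chronological order". Section 6.4.6 (Table 3.06, Lupus Impact Tracker by item) lists its time points as "Baseline, Week 24, and Week 52, and at discontinuation/completion (LOCF"). The same list stands in 6.4.3, in 6.4.7 (Table 3.07, laboratory tests), in 6.4.13 (Figure 3.04, Lupus Impact Tracker) and in 6.4.15 (Figure 3.06x, laboratory tests). Section 6.7 repeats Tables 3.03 and 3.07 and Figure 3.06x by baseline steroid category, as Tables 5.03 and 5.04 and Figure 5.02x.

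LLDAS also has an LOCF time point (6.4.2 and 6.4.12). Its definition in 4.10 combines SELENA SLEDAI, PGA, steroid dose, immunosuppressant and other drug use, and adverse events. Item 2 reads "No new signs or symptoms as compared to the last SELENA-SLEDAI assessment".

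**The concern.** One part of the SAP tells the programmer to carry values forward for the Lupus Impact Tracker and the laboratory items, and another part forbids it. The choice decides which patients are in the column. If the prohibition is followed, Table 3.03 shows three measures side by side at one labelled time point. Two of them describe nearly the whole assessed population and the third describes mainly patients who stopped treatment. A reader comparing disease activity with patient-reported impact at that time point would be comparing different groups of patients. The laboratory outputs would have the same fault.

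Both readings can be defended from the text, so two programmers could produce different tables from the same plan. Effectiveness is part of the stated study objective, and Protocol section 9 names the Lupus Impact Tracker and the laboratory items among the effectiveness analyses.

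**Working it through.** The plan states no figure on this point, so there is none to reproduce. The check compares passages and adds a simple illustration of column size.

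**1. Who has a true discontinuation/completion value?** Protocol section 8 (items 11 and 12) collects these measures at the start, at Weeks 24 and 52, or on stopping. SAP 4.18 reclassifies patients whose treatment ended at or after 52 weeks as continuing. A recorded stopping value therefore exists essentially only for patients who stopped before Week 52.

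**2. What happens to a continuing patient with no such record?**

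| Measure | Rule that applies | Patient in the LOCF column? |
|---|---|---|
| SELENA SLEDAI, PGA | 4.4.2: filled from data up to Week 52 | Yes |
| Lupus Impact Tracker, laboratory items | 4.4.1 bars filling; 4.4.3 drops the missing time point | No |

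**3. Does another rule cover the gap?** The SAP fills in values elsewhere. It does so for dates (4.4.5, 4.5), for absent steroid information (4.12) and for early stoppers in the Week 40 to 52 steroid endpoint (4.10). None of these covers Lupus Impact Tracker or laboratory values.

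**4. Column size.** Inputs:
- N = 600, the target for the safety analysis set (Protocol section 4). It is illustrative only, because the efficacy set is a subset.
- d = share stopping before Week 52. This is not in the documents and is assumed to be 10% to 40%.

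Maximum column size is d × N without carrying forward, and N with it.

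| Assumed d | Lupus Impact Tracker or laboratory, as written | SELENA SLEDAI or PGA |
|---|---|---|
| 10% | 0.10 × 600 = 60 | up to 600 |
| 20% | 0.20 × 600 = 120 | up to 600 |
| 30% | 0.30 × 600 = 180 | up to 600 |
| 40% | 0.40 × 600 = 240 | up to 600 |

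Up to 600 means patients with a baseline and at least one post-baseline value.

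**5. Effect on a mean.** Let m_s and m_c be the mean changes in stoppers and continuers. The column as written estimates m_s. With carrying forward it estimates (1 − d)·m_c + d·m_s. The difference is (1 − d)(m_s − m_c). The documents give neither mean, so its size cannot be calculated. It vanishes only if stoppers and continuers change alike.

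**6. Baseline.** Section 4.4.2 sets an upper limit of Week 52 and no lower limit. Section 4.10 requires a post-treatment assessment for responders, but the summary statistics in 6.4.3 carry no such condition.

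**7. LLDAS.** Section 4.4.2 can fill its SELENA SLEDAI and PGA parts. No rule says that both must come from one date, or which earlier assessment item 2 uses when the SELENA SLEDAI record is itself carried forward. The LOCF status is therefore not fully defined.

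**The case against.** The strongest reply is that this is a heading left incomplete. SAP section 3 spells out the abbreviation LOCF, so labelling a time point with it is already an instruction to carry forward. The change-history entry for version 2.0 mentions an imputation method that included the Lupus Impact Tracker. The summary statistics in 5.1 include the sample size, so a shrunken column would be visible in the tables. Weeks 24 and 52 are reported separately, and the main response rate uses SELENA SLEDAI, which 4.4.2 covers. The mock tables, which might settle the matter, are not among the documents.

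Much of this stands. Carrying forward was probably intended, the outputs are descriptive, and n would give a warning. But the change history describes superseded text and can only hint at intent, while the prohibition in 4.4.1 is explicit and current. A visible n shows that the groups differ without making them comparable.

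A reader might also infer more about LLDAS than the text supports:

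- **That item 2 is empty for carried records.** This follows only if a carried record is compared with itself. The more natural reading is comparison with the preceding assessment, and nothing specifies self-comparison.
- **That a later steroid dose is joined to an earlier score.** Item 4 of the definition ties the dose to the time of assessment, and 4.12 uses the seven days ending on the evaluation day.
- **That mixed dates are common.** Protocol section 8 schedules SELENA SLEDAI and PGA together, so a mixed pair needs one to be recorded without the other.
- **That confidence intervals rest on the faulty columns.** Section 6.4.2 says "95% confidence intervals will be calculated for assessment at discontinuation/completion (LOCF"), but that covers responder rates. No interval is specified for the Lupus Impact Tracker or the laboratory items.

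**Conclusion.** The contradiction is in the current SAP and no other section resolves it. Followed literally, the stated rule changes the population of the LOCF column for the Lupus Impact Tracker and the five laboratory items. They would be shown for mainly early stoppers, against nearly all assessed patients for SELENA SLEDAI and PGA. For an assumed 10% to 40% stopping before Week 52 and an illustrative 600 patients, that is about 60 to 240 against up to 600. Both inputs are illustrative. The shift in mean scores, and any overstatement of LLDAS, cannot be given a number from the documents.

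For LLDAS the finding is narrower: the reference date and the item 2 comparator are not stated at the LOCF time point. The documents do not show that the definition fails. The point should be corrected because the affected tables are named effectiveness outputs and the remedy is cheap. It does not touch the sample size, the safety analyses or the SELENA SLEDAI response rate.

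**What to change.** 1. Extend 4.4.2 to the Lupus Impact Tracker and to anti-dsDNA antibody, C3, C4, CH50 and the protein/creatinine ratio. Carry forward the last post-baseline value up to Week 52, and state that baseline values are never carried forward. Alternatively, remove the LOCF label and column for these measures from Tables 3.03, 3.06, 3.07, 5.03 and 5.04 and Figures 3.04, 3.06x and 5.02x.
2. For LLDAS at the LOCF time point, state that all components are read at one common assessment date, and that item 2 is judged against the assessment before the carried one.
3. If the tables have already been run, state in the final report which rule was applied, and show n for each measure and time point.

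The cost is a wording change and minor reprogramming, with no new data. Slightly fewer patients would have an LLDAS status at the LOCF time point, because a common date is required.

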4.4.2. SELENA SLEDAI, PGA

With the LOCF approach, if there is no data at the time of discontinuation/completion after Week 52 or Week 24 from the start of administration of this drug, the data will be imputed with the data up to Week 52 from the start of administration of this drug.

4.4.3. Missing continuous data

If there is a missing value in the tabulation of continuous data, it will be excluded from the tabulation. If continuous data are available at multiple time points, only the missing time points will be excluded. If continuous data are classified into categories, follow "4.4.4 Categorical Data."

4.4.4. Categorical data

- ✧ Data should be handled as "unknown" regardless of whether it is missing, unknown, or not recorded.
(Excluding those defined in 4.6. Handling of presence/absence)
- ✧ Unless otherwise specified, missing values will be included in the denominator of percentages.
- ✧ Odds ratio excludes unknown category.

4.4.5. Date Variables

Imputation of date variables will be handled as follows.

< End date of administration of this drug >

- ✧ If the number of doses of this drug is once, imputation will use the start date of this drug administration.

< Adverse events >

- ✧ If the date of onset and date of outcome are missing, they will not be imputed and will be handled as unknown.

< Prior treatment drugs/Prior treatment (other than drugs)/Concomitant drugs >

- ✧ Only systemic steroids for SLE have a date but if the last record is ' Dosing Continued ', then it will be imputed with the last date from this drug Administration Status.

4.5. Treatment Disposition Date for Continued Treatment

The end date of administration in the case of continued administration will be imputed with the last date of administration in this drug administration status. However, if the administration status of this drug is blank, it will be handled as follows.

Date of completion of treatment = date of initiation of treatment + < number of days considered to be converted > -1

Deemed equivalent number of days

24 weeks → 168 days (when only CRF 1 is collected)

52 weeks → 364 days

*If the end date of administration calculated above is after the end date of the contract period, it will be

complemented with the end date of the contract.

4.6. Handling of presence/absence

Presence/absence shall be handled as follows.

Description of the column for presence/absence	Detailed item record	Handling of presence/absence
No	No	Should be "No."
	Yes	Should be "Yes."
Yes	No	Should be ' Unknown ' .
	Yes	Should be "Yes."
Unknown/not specified	No	Should be ' Unknown ' .
	Yes	Should be "Yes."

The target shall be the adverse event field, and other items shall be judged based on the presence or absence of detailed description.

Checkboxes for drug category and drug name should be handled as described above.

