Identification number, gender, year of birth or age, start date of administration of Benlysta, reason for use of Benlysta (including the presence or absence of severe lupus nephritis, severe CNS lupus), autoantibody associated with SLE (type, presence or absence of "positive"), disease duration of SLE, body weight, presence or absence of vaccination (24 weeks before the start of administration), type of vaccine and date of vaccination, past history

(TB, HB), presence or absence of comorbidities (HB, renal impairment, hepatic impairment, allergy, others) and name of comorbidities

<Definition of severe lupus nephritis, severe CNS lupus>

- Severe lupus nephritis
Lupus nephritis with a proteinuria level of >6 gm/24 hours or equivalent according to a spot urine protein/creatinine ratio or a serum creatinine level of >2.5 mg/dl
- Severe CNS lupus
CNS lupus with seizure, psychosis, organic brain syndrome, cerebrovascular accident, encephalitis or CNS vasculitis

To protect the confidentiality regarding identification of an individual patient, the identification number should be a unique number assigned to an individual patient by the investigator, etc.

In this study, any disease, symptom, and allergy history which is present before the start of administration of Benlysta except SLE will be handled as a “comorbidity”.

The disease activity and diseased organ systems will be defined by SELENA SLEDAI score at the start date of administration (specified in "11. Course of clinical symptoms" section).

3. Screening test regarding TB before the start of administration

Presence or absence, and results of chest image test, tuberculin reaction, interferon-gamma release assay

(The chest image test includes the presence or absence of findings of old TB.)

<Related descriptions in the Package Insert (For details, see the latest Package Insert)>

<Revised: October 2019 (Version 4), excerpts from the Package Insert>

2. IMPORTANT PRECAUTIONS (for intravenous use)*

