- Past history (Tuberculosis, hepatitis B)

If multiple symptoms are selected, they will be counted multiple times.

- Mean daily dose of steroid at the start of treatment [mg/day] (0, 0< to ≤ 7.5, 7.5<, unknown)
- Mean daily dose of steroid at the start of treatment 2 [mg/day] (0, 0< to ≤ 5, 5< to ≤ 10, 10<, unknown)

- Pregnancy (No, Yes)
- Prior treatment for SLE (Steroids, immunosuppressants, antimalarials, NSAIDs, other biologics, cyclophosphamide intravenous injection) (No, Yes)
- Prior medications for SLE (Steroids, immunosuppressants, antimalarials, NSAIDs, other biologics, cyclophosphamide intravenous injection)
- Presence or absence of concomitant medication (No, Yes)
- Concomitant medication for SLE (Steroids, immunosuppressants, antimalarials, NSAIDs, other biologics, cyclophosphamide intravenous injection) (No, Yes)
- Details of concomitant medications for SLE (Steroids, immunosuppressants, antimalarials, NSAIDs, other biologics, cyclophosphamide intravenous injection)
- Presence or absence of concomitant therapy (No, Yes)
- Complications (No, Yes)
- Presence or absence of complication (renal impairment) (No, Yes)
- Presence or absence of complication (hepatic impairment) (No, Yes)
- Complication (allergy) (No, Yes)
- Status of administration of this drug at the end of the observation period (Continuation of administration, discontinuation/completion of administration)

< Summary statistics >

	
 • Age [years] • Age [years] (children: < 15 years) • Age [years] (elderly: ≥ 65 years) • Mean daily dose of steroid at the start of treatment [mg/day] • Duration of SLE [year] • Weight [kg]
Baseline	
< Category >
 
 • SELENA SLEDAI score (≤ 9, $10 \leq$, unknown) • Each item of SELENA SLEDAI • PGA score ($0 \leq$ to ≤ 1, $1 <$ to ≤ 2.5, $2.5 <$ to ≤ 3, unknown)
	
< Summary statistics >
 
 • SELENA SLEDAI score • PGA score • Lupus Impact Tracker
Laboratory	< Category >
Evaluations	
 • Anti-dsDNA antibody [IU/mL] (Negative, Positive (≥ 30 IU/mL), Unknown) • Complement Levels: 
 Low C3 and/or Low C4 Other than the above Unknown • C3 (baseline) [mg/dL] (<90, $90 \leq$, unknown) • C4 (baseline) [mg/dL] (<10, $10 \leq$, unknown)

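### For coded comorbidities, SAP 4.6 looks only at written detail, so a ticked 'Yes' with no disease name, or a blank answer, most naturally lands in 'No' instead of 'Unknown'

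*SAP*

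**What the plan says.** Protocol section 8, item 2, collects two things for each patient: "presence or absence of comorbidities (HB, renal impairment, hepatic impairment, allergy, others) and name of comorbidities". The yes/no answer and the name are separate pieces of information.

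SAP 4.6 tabulates how a presence/absence column and its detail record combine. Detail present always gives 'Yes'. Without detail, a 'No' answer stays 'No', while a 'Yes' answer and an unknown or unspecified answer both become 'Unknown'. The grid is then limited: "The target shall be the adverse event field, and other items shall be judged based on the presence or absence of detailed description". A further sentence reads "Checkboxes for drug category and drug name should be handled as described above", without saying whether it points to the grid or to the detail-only rule.

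SAP 4.4.4 sends categorical data to 'unknown' "regardless of whether it is missing, unknown, or not recorded", but with a carve-out: "Excluding those defined in 4.6. Handling of presence/absence". It adds: "Odds ratio excludes unknown category".

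SAP 6.2.1 lists the renal row as "Presence or absence of complication (renal impairment) (No, Yes", with no third level. Complications overall, hepatic impairment and allergy are listed the same way. SAP 4.9 assigns renal, hepatic and allergic conditions from MedDRA-coded terms, which requires a written name.

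**The concern.** The plan recognises, for adverse events, that a tick without detail or an empty answer does not establish absence. For comorbidities it sets the answer aside, so a patient whose physician ticked 'Yes', or gave no answer, is most naturally counted as free of the condition.

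These rows are used downstream. Renal and hepatic impairment are among the specific backgrounds for the event tables in SAP 6.3.3 and 6.3.6. The complication rows feed ADR incidence by background (SAP 6.3.1) and response rate by background (SAP 6.4.1). Protocol 9.2 calls for odds ratios on factors that may affect safety and effectiveness, and Protocol 13 links risk factors to possible revision of the Package Insert. Since Protocol 8 asks for items only as far as possible, some incomplete fields should be expected. Under the detail-only rule they leave no trace in the tables.

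**Working it through.** **Step 1: the two rules side by side.** The documents give no figure for this point, so the first check is to list every combination.

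| Answer | Detail | Grid (adverse events) | Detail-only rule (other items) |
|---|---|---|---|
| No | No | No | No |
| No | Yes | Yes | Yes |
| Yes | No | Unknown | No (inferred) |
| Yes | Yes | Yes | Yes |
| Unknown/blank | No | Unknown | No (inferred) |
| Unknown/blank | Yes | Yes | Yes |

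The rules differ in two of six cells. 'No' in those cells is inferred from three places: the two-state rule in 4.6, the carve-out in 4.4.4, and the two levels in 6.2.1.

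**Step 2: size in one illustration.** All inputs are assumed: prevalence 20%; 10% of patients with the condition lack detail; ADR risk 10% with the condition and 5% without; lack of detail unrelated to the outcome.

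- True odds ratio: (0.10/0.90) / (0.05/0.95) = 2.11.
- Share moved to 'No': 0.20 × 0.10 = 0.02, or 12 of 600 patients. 'Yes' becomes 18% and 'No' 82%.
- Risk in the 'No' group: (0.80 × 0.05 + 0.02 × 0.10) / 0.82 = 0.042/0.82 = 5.12%.
- Odds ratio under the detail-only rule: (0.10/0.90) / (0.0512/0.9488) = 2.06.
- With the 2% coded 'Unknown' and excluded, the odds ratio returns to 2.11.

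**Step 3: a range.** Take N = 600, a risk of 5.3% without the condition (borrowed from the serious-infection rate in Protocol 4) and an assumed true odds ratio of 2.0. Let a and b be events and non-events with the condition, c and d those without it, and f₁ and f₀ the shares lacking detail among a and b.

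- Detail-only: a(1−f₁)(d + b·f₀) / [b(1−f₀)(c + a·f₁)].
- Unknown excluded: a(1−f₁)d / [b(1−f₀)c] = 2.0 × (1−f₁)/(1−f₀).

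At 20% prevalence, a = 12.08, b = 107.92, c = 25.44 and d = 454.56. With f₁ = f₀ = 0.1: (10.87 × 465.35) / (97.13 × 26.65) = 1.95 (1.955 before rounding of the inputs).

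| Lacking detail | 20% prevalence: detail-only | 40% prevalence: detail-only | Unknown excluded |
|---|---|---|---|
| 10% of all with condition | 1.955 | 1.888 | 2.00 |
| 20% of all | 1.913 | 1.798 | 2.00 |
| 30% of all | 1.875 | 1.725 | 2.00 |
| 20% of non-events only | 2.619 | 2.817 | 2.50 |
| 20% of events only | 1.461 | 1.277 | 1.60 |

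In the last two rows the larger part of the shift comes from outcome-dependent loss of detail, which recoding does not cure. Coding as 'Unknown' is still nearer to 2.0 in each.

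**The case against.** **'No' is not printed for other items.** This stands. The carve-out in 4.4.4 could be read as covering only the adverse event grid, leaving missing comorbidity as 'unknown'. Gender is also listed with two levels, so a missing third level is weak evidence by itself. Vaccination status lies outside the adverse event field yet keeps 'unknown', which fits poorly with a strict two-state rule. The 'No' reading remains the most natural one for the coded comorbidities, and the text needs settling either way.

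**There is a design reason for requiring detail.** A tick without a term cannot be checked against the MedDRA groupings in SAP 4.9 or placed in the SOC and PT rows of Table 1.03x. That is a good reason not to count it as 'Yes'. It is not a reason to count it as 'No'.

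**Does this reach TB and hepatitis B history?** A reader might infer so. SAP 6.2.1 counts past history by what is selected, the selection may itself be the detail, and the CRF is not available. Comorbid hepatitis B is defined by reference to the study plan, not by a coded grouping. The documents do not support extending the ticked-'Yes' problem to these items.

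**Do poor forms fill the 'No' group with under-reported events and inflate odds ratios?** A reader might infer this too. Moving only the ticked-'Yes' patients, with their recorded events halved, gives (0.80 × 0.05 + 0.02 × 0.05) / 0.82 = 5.0% and leaves the odds ratio at 2.11. Inflation needs a further assumption: patients without the condition who left the answer blank and also under-report events. If they ticked 'No', the grid would code them 'No' as well. Exclusion S5 in SAP 4.3.1 already removes patients whose adverse event answer is unknown or blank with no event data.

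**The factor analysis is not visible.** SAP 5.4 is redacted, so which comorbidities enter odds ratios, and against what reference, cannot be confirmed. The tables by background are affected regardless.

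**Conclusion.** The point holds as a minor one. For coded comorbidities the SAP discards an answer that the protocol collects, and its most natural reading places patients with a reported or undetermined condition in the comparison group. The SAP's own grid treats the same cells as 'Unknown' for adverse events.

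When lack of detail is unrelated to outcome, the odds ratio is pulled toward 1: from 2.11 to 2.06 in the main illustration, and from 2.00 to between 1.96 and 1.73 over 10% to 30% lacking detail and 20% to 40% prevalence. Every input on prevalence, risk difference and missing detail is an assumption. The documents do not establish that miscoding has occurred, how often it would occur, or that any conclusion would change.

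**What to change.** - In SAP 4.6, apply the existing grid unchanged to complications overall, renal impairment, hepatic impairment and allergy: 'Yes' without detail gives 'Unknown', and blank or unknown without detail gives 'Unknown'.
- Add an 'unknown' row for these items in SAP 6.2.1 and the tables that depend on it, and let 4.4.4 exclude it from odds ratios.
- Report how many patients fall in each of the six answer-by-detail cells for each item.
- Reconcile 4.6 with the vaccination row that keeps 'unknown', and state which rule the sentence on drug checkboxes refers to.
- Apply the same handling to TB and hepatitis B history only if the CRF has a separate presence/absence answer for them.

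The cost is a sentence in the SAP and a recode of data already collected. The downside is a small 'unknown' row and slightly fewer patients in the odds ratios. If the final tables have already been run, the cell counts and one sensitivity recode would show whether the choice mattered.
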